### Non-Target Lesion Time Point Response (TPR)

---

Complete Response (CR)	

Disappearance of all non-target lesions. All lymph nodes must be non-pathological in size (<10 mm short axis)

Non-CR / Non-PD	

Persistence of one or more non-target lesion(s).

Progressive Disease (PD)	

Unequivocal progression of non-target lesions. Unequivocal progression should normally trump target lesion status. It must be representative of overall disease status change, not a single lesion increase

Not Applicable (NA)	

No non-target lesions identified at screening

Unable to Evaluate (UE)	

One or more non-target lesions are not imaged and the remaining non-target lesions do not meet the criterion for PD.

---

---

**New Lesion Time Point Response (TPR)**

---

Yes	

• Lesion present at follow-up visit either for the very first time or re-appearing (ie, lesion was present at baseline, disappeared at a follow-up visit and re-appeared later). On bone scan, a single new lesion may not be sufficient to qualify as PD. Confirmation should be obtained by performing CT or MRI of the area of concern to confirm ambiguous results of bone scan. Preferred method for confirmation is MRI.

No	

• No new lesions present at follow-up.

Unable to Evaluate (UE)	

• Subject not assessed or incompletely assessed for new lesions.

---

### **Evaluation of Overall Timepoint Response (TPR)**

Target Lesion TPR	Non-target lesion TPR	New lesion TPR	Overall TPR
CR	CR or NA	No	CR*
CR	Non-CR/non-PD	No	PR*
CR	UE	No	PR*
PR	Non-PD or NA or UE	No	PR*
SD	Non-PD or NA or UE	No	SD
UE	Non-PD	No	UE
PD	Any	No or Yes or UE	PD
Any	PD	No or Yes or UE	PD
Any	Any	Yes	PD
NA	CR	No	CR*
NA	Non-CR/Non-PD	No	Non-CR/non-PD
NA	UE	No	UE
Non-PD	Non-PD	UE	UE

CR, complete response; PR, partial response; SD, stable disease; PD, progressive disease, UE, unable to evaluate; NA, not applicable (no such lesions at screening); Any, CR, PR, SD, PD, NA, or UE.

The overall response at a given time point does not depend upon the overall response assigned at any prior time point.

\*Subjects with an overall response of CR or PR must have a repeat tumor assessment performed no less than 4 weeks after the criteria for response are first met. However, the presence or absence of confirmation is not considered when assigning a time point response.

### **Confirmation**

The main goal of confirmation of objective response is to avoid overestimating the response rate observed. For subjects with an overall response of PR or CR at a given time point, changes in tumor measurements must be confirmed by repeat assessments that should be performed no less than 4 weeks after the criteria for response are first met. However, the presence or absence of confirmation is not considered when assigning a time point response. Longer intervals as determined by the study protocol may also be appropriate.

**Best Overall Response**

Best overall response, incorporating confirmation requirements, will be derived during statistical analysis from the series of time point responses and need not be considered when assigning response at each time point.

**Appendix H: EuroQol questionnaire EQ-5D-5L, USA (English) sample version**

Under each heading, please check the ONE box that best describes your health TODAY

**MOBILITY**

- I have no problems walking
- I have slight problems walking
- I have moderate problems walking
- I have severe problems walking
- I am unable to walk

**SELF-CARE**

- I have no problems washing or dressing myself
- I have slight problems washing or dressing myself
- I have moderate problems washing or dressing myself
- I have severe problems washing or dressing myself
- I am unable to wash or dress myself

**USUAL ACTIVITIES** (*e.g. work, study, housework, family or leisure activities*)

- I have no problems doing my usual activities
- I have slight problems doing my usual activities
- I have moderate problems doing my usual activities
- I have severe problems doing my usual activities
- I am unable to do my usual activities

**PAIN / DISCOMFORT**

- I have no pain or discomfort
- I have slight pain or discomfort
- I have moderate pain or discomfort
- I have severe pain or discomfort
- I have extreme pain or discomfort

[figure not shown]
**ANXIETY / DEPRESSION**

- I am not anxious or depressed
- I am slightly anxious or depressed
- I am moderately anxious or depressed
- I am severely anxious or depressed
- I am extremely anxious or depressed

- We would like to know how good or bad your health is TODAY.
- This scale is numbered from 0 to 100.
- 100 means the best health you can imagine.  
0 means the worst health you can imagine.
- Mark an X on the scale to indicate how your health is TODAY.
- Now, please write the number you marked on the scale in the box below.

YOUR HEALTH TODAY =

**The best health  
you can imagine**

**The worst health  
you can imagine**

USA (English) © 2009 EuroQol Group. EQ-5D™ is a trade mark of the EuroQol Group

# LIST OF ABBREVIATIONS

AE	Adverse event		
AFP	Alpha fetoprotein		
ALP	Alkaline phosphatase		
ALT	Alanine aminotransferase		
AST	Aspartate aminotransferase		
ATA	Adequate tumor assessment		
ATC	Anatomical Therapeutic Chemical		
BLQ	Below limit of quantitation		
BMI	Body mass index		
BSAP	Bone-specific alkaline phosphatase		
BUN	Blood urea nitrogen		
CI	Confidence interval		
СМН	Cochran-Mantel-Haenszel		
CRF	Case report form		
СТ	Computerized tomography		
CTC	Circulating tumor cell		
CTCAE	Common terminology criteria for adverse events		
CTMS	Clinical trial management system		
СТх	C-terminal cross-linked telopeptides of type I collagen		
DBP	Diastolic blood pressure		
EBRT	External beam radiation therapy		
ECOG PS	Eastern Cooperative Oncology Group Performance Status		
ER	Emergency room visit		
FDA	Food and Drug Administration		
GGT	Gamma-glutamyltransferase		
HBCAB	Hepatitis B core antibody		
HBsAg	Hepatitis B surface antigen		
HBV	Hepatitis B virus		
НСС	Hepatocellular carcinoma		
HCRU	Health care resource utilization		
HCV	Hepatitis C virus		

HGB	Hemoglobin
HbA1c	Glycated hemoglobin
HR	Hazard ratio
HRQOL	Health Related Quality of Life
ICH	International Conference on Harmonization
ICU	Intensive care unit
IDMC	Independent Data Monitoring Committee
INR	Prothrombin International normalized ratio
ITT	Intent-To-Treat
IVRS	Interactive Voice Response System
IWRS	Interactive Web Response System
LDH	Lactate dehydrogenase
LLN	Lower limit of normal
LLQ	Lower limit of quantitation
MRI	Magnetic resonance imaging
MedDRA	Medical Dictionary for Regulatory Activities
NPACT	Non-protocol anti-cancer therapy
NTx	N-terminal cross-linked telopeptides of type I collagen
OS	Overall survival
ORR	Objective response rate
PD	Progressive Disease
PFS	Progression-free survival
PK	Pharmacokinetic
PP	Per-protocol
qd	Once daily
QOL	Quality of Life
SAE	Serious adverse event
SBP	Systolic blood pressure
SAP	Statistical analysis plan
SD	Stable Disease
TEAE	Treatment emergent-adverse event
TSH	Thyroid-stimulating hormone

UE	Unable to evaluate
ULN	Upper limit of normal
ULQ	Upper limit of quantitation
UPCR	Urine protein/creatinine ratio
VAS	Visual analogue scale
WHO-DD	World Health Organization drug dictionary

# 1 ADMINISTRATIVE STRUCTURE AND VERSION HISTORY

This study is being conducted under the sponsorship of Exelixis, Inc. Statistical programming and analyses are being conducted under contract by PPD in conjunction with Exelixis, Inc.

This version of the Statistical Analysis Plan (SAP) is based on amendment 1.0 of the protocol dated 23, April 2014.

**Table 1: Protocol Version History** 

Date	Version	Primary Reason(s) for Amendment
12 March 2013	Original Protocol	Not Applicable
23 April 2014	Amendment 1.0	Provides additional clarification to 3 inclusion criteria and 4 exclusion criteria.
		Additional Child-Pugh testing time-points have been added.
		Specifies that all subjects will have hepatitis virus testing via central laboratory prior to enrollment but those results will not be required for randomization.
		Introduces the Maintenance Phase, which subjects will enter when sufficient data have been collected to evaluate all study endpoints.

### 2 STUDY DESCRIPTION

# 2.1 Study Design

This is a Phase 3 multicenter, randomized, double-blinded, controlled trial of cabozantinib vs. placebo, both with best supportive care, in subjects with advanced hepatocellular carcinoma (HCC) who were previously treated with sorafenib. The primary efficacy endpoint for the study is overall survival (OS). Approximately 760 subjects will be randomized in a 2:1 ratio to receive either cabozantinib or placebo.

Each subject's course of treatment will consist of the following periods:

Pre-treatment Period: Potential subjects will be screened to determine if they meet the required eligibility criteria. Qualifying screening assessments must be performed within 28 days before randomization unless otherwise specified.

Treatment Period: Subjects who meet all study eligibility criteria, in addition to receiving best supportive care, will be randomly assigned in a 2:1 ratio to the cabozantinib and placebo arms respectively. Crossover between treatment arms will not be allowed.

Subjects will receive blinded study treatment and best supportive care as long as they continue to experience clinical benefit in the opinion of the investigator or until there is unacceptable toxicity or the need for subsequent systemic anti-cancer treatment or liver-directed local anti-cancer therapy. Study treatment may even continue after radiographic progression as long as the investigator believes that the subject is still receiving clinical benefit and that the potential benefit of continuing study treatment outweighs potential risk.

When sufficient data have been collected to evaluate all study endpoints and upon site notification from the Sponsor, subjects remaining on study treatment will enter the study Maintenance Phase. In this phase subjects will continue to receive study treatment until a criterion for protocol-defined discontinuation has been met. Subjects will undergo safety assessments and tumor assessments per standard of care.

Post-Treatment Period: The final safety assessment will occur at the post-treatment follow-up visit 30 (+14) days after the date of the decision to discontinue treatment unless a Grade 3/4 AE or an SAE is determined to be ongoing.

Radiographic tumor assessments and EQ-5D-5L quality of life (QOL) assessments will continue per the protocol-defined schedule, regardless of whether study treatment is given, reduced, interrupted, or discontinued until the later of 8 weeks after radiographic progression per RECIST 1.1 as determined by the investigator or the date of the decision to permanently discontinue study treatment.

Subjects will additionally be contacted approximately every 8 weeks after the post-treatment follow-up visit to assess survival status and to document receipt of subsequent anti-cancer therapy. Every effort will be made to collect these protocol-specific evaluations unless consent to participate in the study is withdrawn.

The study design, schedule of the visits, assessments and conduct are described in the study protocol.

# 2.2 Study Treatment

Eligible subjects will be randomized in a 2:1 ratio to the following treatment arms:

- Cabozantinib arm: Oral cabozantinib (60 mg) qd
- Placebo arm: Oral cabozantinib-matched placebo qd

In addition, all subjects will also receive best supportive care.

# 2.3 Study Objectives and Endpoints

The primary objective of this study is to evaluate the effect of cabozantinib compared with placebo on overall survival in subjects with advanced HCC previously treated with sorafenib.

# 2.3.1 Primary Efficacy Endpoint

The primary efficacy endpoint is overall survival (OS) (see section 7.1.1 for definition).

# 2.3.2 Secondary Efficacy Endpoint

The secondary efficacy endpoints are:

- Objective response rate (ORR) per RECIST 1.1 (see section 7.1.1)
- Progression-free survival (PFS) per RECIST 1.1 (see section 7.1.1)

### 2.3.3 Additional Endpoints

The following endpoints are discussed in their respective sections:

- Safety and tolerability (see section 8)
- Relationship of baseline and changes in biomarkers with treatment and/or clinical outcome (see section 7.5)
- Health-related quality of life (HRQOL) as assessed by the EuroQol Health questionnaire instrument (EQ-5D-5L) (see section 7.5.1)
- Pharmacokinetics (PK) (see section 7.5.7)

# 2.4 Power and Sample Size Justification

For the primary OS endpoint, up to three event-driven analyses are planned at 50%, 75%, and 100% information fraction (311, 466, and 621 deaths, respectively). A sample size of 760 subjects with a total of 621 events (and two interim analyses) provides the study with 90% power for a 2-sided log-rank test at 5% level of significance to detect a 31.6% increase in OS (HR = 0.76). Assuming a median OS of 8.2 months in the placebo arm (based upon the BRISK trial; Llovet 2012) and exponential distribution, this corresponds to median OS of 10.8 months in the cabozantinib arm.

In the current design, the minimum observed effect that would result in statistical significance for OS at the two interim and final analyses are 42.1% improvement (HR = 0.70, from 8.2 to 11.7 months), 25.7% improvement (HR = 0.80, from 8.2 to 10.3 months) and 18.4% improvement (HR = 0.84, from 8.2 to 9.7 months), respectively.

With an average accrual rate of 31.5 subjects per month and using a 2:1 treatment allocation ratio, an approximate total of 760 subjects (507 subjects in cabozantinib arm and 253 subjects in placebo arm) are required to observe the minimum number of events within the planned study duration (25 months accrual and approximately 38 months to observe the required events for OS). Currently since the average accrual rate is less than 31.5 subjects per month this will also prolong the study duration and time required to observe the required events for OS.

Power and sample size estimates were calculated using EAST v5 by Cytel Software.

# 2.5 Randomization and Blinding

This is a randomized, double-blinded, controlled trial of cabozantinib versus placebo. cabozantinib-matched placebo will be packaged and color-, size-, and shape-matched to be indistinguishable from cabozantinib.

Study treatment assignment will be unknown to the subjects, investigators, study centers, the Sponsor, and any contract research organization affiliated with the study other than those authorized to access treatment assignment for regulatory safety reporting and submission processes (see Section 8.2.2 of Protocol), IVRS or IWRS system administration and drug supply management.

When an individual subject has been deemed eligible at the study site, the site representative will use the designated interactive voice response system/interactive web response system (IVRS/IWRS) to enroll the subject into the study. Eligible subjects will be randomly assigned in a 2:1 ratio to the cabozantinib and placebo arms.

Randomization will be stratified by the following factors:

- etiology of disease (HBV [with or without HCV], HCV [without HBV], or Other),
- geographic region (Asia [includes Japan, Hong Kong, South Korea, Singapore, Malaysia, Philippines, Taiwan, Thailand, Vietnam], Other Regions)
- presence of extrahepatic spread of disease and/or macrovascular invasion (Yes, No).

Note that IVRS/IWRS will be referred as IxRS in this document and HBV refers to hepatitis B virus and HCV refers to hepatitis C virus.

### 3 ANALYSIS POPULATIONS

#### 3.1 Intent to Treat

The Intent-To-Treat (ITT) population is defined as all randomized subjects regardless of whether any study treatment or the correct study treatment was received. This population will be used for efficacy analyses.

# 3.2 Safety Population

The Safety population will include all randomized subjects who receive any amount of study treatment (either cabozantinib or cabozantinib-matched placebo). Analyses based on the Safety population will be performed according to the actual treatment received. Subjects randomized to the placebo arm who receive any amount of cabozantinib in error will be summarized in the cabozantinib group.

### 3.3 Per Protocol Population

A Per Protocol population is not defined or planned for the study.

### 4 GENERAL CONVENTIONS

The statistical principles applied in the design and planned analyses of this study are consistent with International Conference on Harmonization (ICH) E9 guidelines (ICH 1998).

Continuous data will be summarized using descriptive statistics (number of observations, mean, standard deviation, median, 25th and 75th percentiles, minimum, and maximum). Frequencies and percentages will be used for summarizing categorical (discrete) data.

Confidence intervals, when presented, will generally be constructed at the 95% level. For binomial variables, the normal approximation methods will be employed unless otherwise specified.

A month is operationally defined to be 30.4375 days. Six months is operationally defined to be 183 days.

All summaries will be presented by treatment arm unless otherwise specified.

#### 4.1 **Definition of Baseline**

In general, for efficacy endpoints the last observed measurement prior to randomization will be considered the baseline measurement. Exception to this rule are efficacy markers such as pharmacogenetics blood samples, biomarker samples, bone marker samples and blood samples for potential circulating tumor cell (CTC) analyses. These samples per schedule of assessment were collected prior to the first dose date hence the baseline measurements will be with respect to the first dose date. For subjects who did not take any study treatment, any

biomarker sample available prior to randomization will be considered as baseline observation.

For safety endpoints the last observation before first dose of study treatment will be considered the baseline measurement unless otherwise specified. For assessments on the day of first dose where time is not captured, a nominal pre-dose indicator, if available, will serve as sufficient evidence that the assessment occurred prior to first dose.

Assessments on the day of first dose where neither time nor a nominal pre-dose indicator are captured will be considered prior to first dose if such procedures are required by the protocol to be conducted before first dose.

# 4.2 Definition of Study Day

For the purpose of efficacy data summaries, study day is defined with respect to the randomization date. For visits (or events) that occur on or after randomization, study day is defined as (date of visit [event] – date of randomization + 1). For visits (or events) that occur prior to randomization, study day is defined as (date of visit [event] – date of randomization). There is no Study Day 0.

For the purpose of safety data summary, Dose Day 1 is defined as the date of first dose of study treatment (referred to in the protocol as Week 1 Day 1). For visits (or events) that occur on or after first dose, dose day is defined as (date of visit [event] – date of first dose of study treatment + 1). For visits (or events) that occur prior to first dose, dose day is defined as (date of visit [event] – date of first dose of study treatment). There is no Dose Day 0.

For listings (such as for adverse events [AEs]) that include the derivation of "days since last dose," this is defined as (event date – date of last dose). Events that occur on the same day as the last dose of study drug will therefore be described as occurring zero days from the last dose of study drug.

#### 4.3 Visit Window Calculation

Analyses will be according to actual visit dates and times. The planned analyses do not require the calculation of visit windows. However, for analyses that require a particular visit as planned, measurements included in that visit must have occurred during the acceptable window defined for the visit in the protocol, unless otherwise specified in this plan.

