Clinic visits for safety evaluations will occur prior to dosing on W1D1 and at minimum every 2 weeks ( $\pm$  3 days) after treatment is initiated through W9D1 and then every 4 weeks ( $\pm$  5 days) thereafter independent of any dose interruptions. The final safety assessment will occur at the post-treatment follow-up visit 30 (+14 days after the date of the decision to discontinue treatment) unless a Grade 3/4 AE or an SAE is determined to be ongoing (see Section 8.3.4).

If study treatment is interrupted, investigators should perform additional safety assessments weekly or more frequently as clinically indicated. Results of safety assessments should be reviewed as soon as they become available in order to make timely decisions regarding the continuation, interruption, or restarting of study treatment.

Radiographic tumor assessments (Section 5.7.6) and HRQOL assessments (Section 5.7.8) should be performed according to the schedule in Appendix A (Appendix B for the Open-Label Phase, Appendix C for the Maintenance Phase [HRQOL will not be assessed in the Open-Label Phase or Maintenance Phase]).

In accordance with the ITT principle, HRQOL, and radiographic tumor assessments, as well as survival follow-up, are to be performed per protocol even for subjects randomized but who never receive study treatment. For such subjects, W1D1 is defined as the date of randomization.

Child-Pugh Score every 8 weeks ( $\pm$  5 d) after randomization (W9D1, W17D1 etc). Child-Pugh assessments should continue regardless of whether study treatment is given, reduced, interrupted, or discontinued until the later of 8 weeks after radiographic progression per RECIST 1.1 as determined by the investigator or the date of the decision to permanently discontinue study treatment. (Please see Appendix B for the Open-Label Phase, Child-Pugh assessments will be discontinued for the Maintenance Phase).

Blood samples for pharmacogenetic, plasma biomarker, serum bone marker analyses, and potential CTC analysis (Section 5.7.11) will be collected according to the schedule in Appendix A. (These assessments will be discontinued for the Open-Label Phase or Maintenance Phase.)

In addition, tumor tissue (archival or recently biopsied) will be obtained (Section 5.7.11) at enrollment whenever available for exploratory analysis of MET and potentially other pathway components or modulators associated with the mechanism of action of cabozantinib as predictive biomarkers.

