Blood samples for determination of plasma concentrations of cabozantinib and potentially relevant metabolites (Section 5.7.10) will be performed according to the schedule in Appendix A. (These assessments will be discontinued for the Open-Label Phase or Maintenance Phase.)

The schedule for assessments should be maintained independent of any dose interruptions.

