## **Appendix A: Schedule of Assessments**

The schedule of required assessments is presented in this appendix. Following randomization, assessments for safety and EQ-5D-5L are to occur corresponding with study weeks [eg, Week 5 Day 1 (W5D1)] which are fixed from Week 1 Day 1 (W1D1) defined as the date of the first dose of study treatment. W1D1 should occur within 3 days after randomization (see Section 6.1). All assessments for radiographic efficacy (CT, MRI, bone scans) will be scheduled based on the date of randomization (see Section 5) and are to be performed even for subjects randomized but never treated. For such subjects, W1D1 is defined as the date of randomization. In the absence of toxicity, all scheduled safety visits should occur within  $\pm 3$  days of the nominal time for the first 9 weeks and within  $\pm 5$  days of the nominal visit day thereafter, unless otherwise indicated. If study treatment is interrupted or missed after W1D1, assessments should continue following the schedule described below.

Unscheduled safety assessments are to be performed weekly or more frequently as clinically indicated. Other unscheduled visits are permitted whenever necessary. See Section 5.6 for further details.

See Appendix B for Schedule of Assessments during the Open-Label Phase and Appendix C for Schedule of Assessments during the Maintenance Phase.

	Pre-randomization	Post-randomization						30-day Post-Treatment Follow-Up (+14 d)	Extended Follow-Up
	Screening (before randomization) a	W1D1 (≤ 3d after randomization)	W3D1 (±3 d)	W5D1 (±3 d)	W7D1 (±3 d)	W9D1 (±3 d)	Beyond Week 9 (±5 d)		
Informed consent (Section 12.2)	X b								
Demographics, medical history, prior cancer TX (Section 5.7.1)	≤ 28 d								
Biopsy to establish histological or cytological diagnosis of HCC (for subjects with no previous histological or cytological diagnosis of HCC; Section 5.1)	X b								
Hep B core antibody, Hep B surface antigen, and Hep C antibody; (Section 5.1)	≤ 28 d								
Child-Pugh Score (Appendix E)	≤ 7 d	Child-Pugh Score every 8 weeks (± 5 d) after randomization (W9D1, W17D1 etc). Child-Pugh assessments should continue regardless of whether study treatment is given, reduced, interrupted, or discontinued until the later of 8 weeks after radiographic progression per RECIST 1.1 as determined by the investigator or the date of the decision to permanently discontinue study treatment							

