## 7.5.1 Health-Related Quality of Life (HRQOL)

Health-related quality of life (HRQOL) will be assessed by the EuroQol Health questionnaire instrument (EQ-5D-5L). The questionnaire will be self-completed by the subjects at various time points until disease progression and will provide a generic measure of health for clinical appraisal (see protocol Section 5.5.8). The EQ-5D-5L questionnaire has two pages: a descriptive page which assesses on an increasing severity scale of 1-5 changes in the following five questions (dimensions): mobility, self-care, usual activities, pain/discomfort, and anxiety/depression. The second page has a 0-100 visual analogue scale (VAS) which records the subjects self-rated health between 100 (best health you can imagine) and 0 (worst health you can imagine) and serves as quantitative measure of health by the subject (see protocol Appendix F and EQ-5D-5L User Guide 2015).

To compare the two treatment arms the following summaries are planned at each time point for each of the 6 questions:

Within each treatment arm:

- Descriptive statistics (number of observations, mean and standard deviation)
- Rate of completion for the questionnaire at each time point. This is defined as total number of subjects who answered all questions on the EQ-5D-5L questionnaire / the expected total number of subjects still on study at the visit

- Mean change from baseline at each time point and the corresponding 95% CI and pvalue from one-sample t-test
- Effect size for change from baseline within arm, calculated as (mean of change in score/pooled standard deviation for baseline scores). An effect size greater than ≥ 0.3 will be considered potentially clinically meaningful
- Shift in the severity scale since baseline

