# 8.3.2 Analysis

All laboratory data parameters and visits will include flags for values above or below laboratory reference ranges. Toxicity grades will be assigned programmatically by applying the CTCAE v4 guidelines. Only results with assessment dates through the end of the safety observation period (see section 4.5) will be tabulated in summary tables.

Laboratory summaries will be presented in SI units. Continuous laboratory test results will be summarized by treatment group using descriptive statistics for actual values and for changes from baseline by scheduled visit. Box-Whiskers plots may also be presented at each scheduled visit (with visits shown on x-axis) for some laboratory parameters. For continuous laboratory test results which are below or above the quantification level, the imputed values as described in Appendix C will be used for deriving the grade and then summarized.

Tables summarizing the incidence of laboratory abnormalities by maximum post-baseline CTCAE grade overall and by baseline grade will be presented. In addition, the following summaries will also be presented:

AlLiver function abnormalities will be assessed as follows:

- Shift from baseline based on normal ranges
- Summaries of subjects meeting Hy's Law laboratory screening criteria as shown below:

```
    >3× ULN (ALT or AST), >2× ULN Total Bilirubin, and <2× ULN ALP

    >3× ULN (ALT or AST), >2× ULN Total Bilirubin, and ≥2× ULN ALP
```

- Sponsor-defined liver function test surveillance criterion:
  - >10× ULN (ALT or AST) and >2× ULN Total Bilirubin
- B] For renal failure surveillance, a summary of subjects meeting renal failure laboratory screening criteria as shown below will be provided:
  - Serum creatinine >= 3.0xULN and >= 2.0x baseline value or
  - eGFR  $\leq$  50% of the baseline value or

- eGFR < 30 mL/min/1.73 m² and ≥ 25% reduction from the baseline value eGFR = 186 x (Creatinine in mmol per L / 88.4)-1.154 x (Age)-0.203 x (0.742 if female) x (1.210 if black) [from the UK CKD eGuide on the Renal Association website: http://egfrcalc.renal.org/]
- C] Categorical summaries for baseline status for TSH and Free T4 will be presented. In addition categorical summaries for post-baseline TSH and Free T4 status among subjects with TSH and Free T4 in the normal range at baseline will also be presented.

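### SAP 4.3 admits only in-window measurements to by-visit summaries; the protocol windows leave gaps, and the SAP gives no fallback for records that fall between them

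*SAP*

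**What the plan says.** SAP section 4.3 opens with a general rule: "Analyses will be according to actual visit dates and times. The planned analyses do not require the calculation of visit windows". A qualification follows, beginning "However, for analyses that require a particular visit as planned". In those analyses the rule is that "measurements included in that visit must have occurred during the acceptable window defined for the visit in the protocol", with an exception where the SAP specifies otherwise. It does not list the analyses that fall under the qualification.

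Several later sections describe by-visit output. Laboratory results are summarized "using descriptive statistics for actual values and for changes from baseline by scheduled visit" (SAP 8.3.2). For EQ-5D-5L, "To compare the two treatment arms the following summaries are planned at each time point for each of the 6 questions" (SAP 7.5.1), and these include two-sample t-tests between arms.

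The protocol states the windows twice. Appendix A introduces them with "In the absence of toxicity, all scheduled safety visits should occur within"; the limits it sets are ±3 days for the first 9 weeks and ±5 days after that. Section 5.2 gives the same ±3 and ±5 days with no reference to toxicity, and describes the later visits as every 4 weeks "thereafter independent of any dose interruptions". It adds: "The schedule for assessments should be maintained independent of any dose interruptions".

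**The concern.** A by-visit summary that accepts only in-window records treats a late but valid measurement as missing at that visit. SAP 4.4 does not impute missing values, so the gap stays open. That is harmless if lateness is unrelated to the patient's condition. It is not harmless if a patient is seen late because of toxicity, since the excluded laboratory value or questionnaire would then reflect the very thing being summarized.

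Toxicity can be expected to differ between an active drug and placebo, and Appendix A's wording allows for toxicity to move a visit. The exclusion could therefore act unequally on the arms. At stake are the by-visit safety tables and the time-point comparisons of quality of life, which protocol 1.4.2 presents as supportive of the primary endpoint.

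**Working it through.** **1. Which summaries need a planned visit.** Laboratory values by scheduled visit (SAP 8.3.2); vital signs at each study visit (8.4.2); EQ-5D-5L at each time point (7.5.1); AFP at each scheduled post-baseline visit (7.5.4); serum bone markers at Weeks 3, 5 and 9 (7.5.5); Child-Pugh shift at each time point (7.5.6). None of these sections sets a wider window or another way of assigning records to visits.

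**2. How much of the calendar the windows cover.** Window width is 2 × tolerance + 1 day: ±3 gives 7 days, ±5 gives 11. Coverage is width divided by visit interval. Intervals and tolerances come from protocol 5.2 and Appendix A.

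| Assessment | Interval (days) | Window (days) | Coverage | Days in no window |
|---|---|---|---|---|
| Safety visits, Week 3 to Week 9 | 14 | 7 | 50% | 7 |
| Safety visits after Week 9 | 28 | 11 | 39% | 17 |
| AFP, Child-Pugh | 56 | 11 | 20% | 45 |
| EQ-5D-5L, Week 5 to Week 9* | 28 | 7 | 25% | 21 |
| EQ-5D-5L after Week 25* | 56 | 11 | 20% | 45 |

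*The EQ-5D-5L row in Appendix A states no tolerance; these lines assume that the column tolerance applies.

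These are calendar shares, not loss rates, because real visits cluster near the target day. They show that a record outside its own window usually lands in no other window.

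**3. The window is not unique at Week 9.** Safety visits at W9D1 carry ±3 days from first dose. AFP and Child-Pugh carry ±5 days from randomization, that is, days 51 to 61. First dose may follow randomization by 0 to 3 days. With no lag the safety window is days 53 to 59, and 4 of the 11 AFP days lie outside it (51, 52, 60, 61). With a 3-day lag it is days 56 to 62, and 5 lie outside (51 to 55). The window in SAP 4.3 has to be defined by assessment.

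**4. The toxicity condition.** Appendix A attaches it to scheduled safety visits only. Protocol 5.2 omits it, and both places require the schedule to be kept when treatment is interrupted. AFP and Child-Pugh have their own ±5 days without it.

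**5. What the exclusion could do to an arm difference.** Let p be the share of records displaced in an arm and d the deficit of displaced records relative to in-window records. The mean of all records is the in-window mean minus p × d, so excluding displaced records raises the arm's mean by p × d. The shift in the arm difference is (p_cabozantinib − p_placebo) × d.

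The documents give neither p nor d. Under assumed values of 15% and 5% displaced and d = 10 EQ-VAS points, the shift is (0.15 − 0.05) × 10 = 1.0 point toward cabozantinib. With placebo at 5%, the assumed range runs from (0.10 − 0.05) × 5 = 0.25 to (0.25 − 0.05) × 20 = 4 points. Equal displacement gives zero, and more displacement on placebo reverses the sign. This shows the mechanism and does not estimate the bias.

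**6. What is not filtered.** Laboratory worst grade and shift in grade use all available results (SAP 8.3.2). So do best and worst changes in AFP and bone markers (7.5.4, 7.5.5) and the EQ-VAS/EQ-Index mixed model (7.5.1), although that model has visit as a fixed effect and the SAP does not say how an off-window record is labelled. AE tables and worst ECOG follow the safety observation period (8.1, 8.5). OS, PFS and ORR follow event or assessment dates.

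**The case against.** The strongest reply is that this is an ambiguity and not an established loss. SAP 4.3 starts from actual dates, confines the filter to analyses that need a planned visit, and allows exceptions elsewhere. The protocol tells sites to keep the schedule through interruptions, and sections 5.2 and 5.6 add weekly or more frequent visits while treatment is held, so toxicity may generate records as well as displace them. Protocol 5.7.8 lets a patient who cannot attend complete the EQ-5D-5L on schedule and return it, so a missed clinic visit need not move the questionnaire. The analyses best suited to showing toxicity are unfiltered, safety has no formal comparison (SAP 8), and exploratory results are descriptive (SAP 7.5). Even the 4-point extreme above is below the SAP's 0.3 effect-size threshold if the EQ-VAS standard deviation is 15 to 25 (assumed), since 0.3 × 15 = 4.5 and 0.3 × 25 = 7.5.

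Most of this stands, and it limits the reach and importance of the point. It does not remove the rule. A table by scheduled visit, or at Weeks 3, 5 and 9, plainly needs a planned visit, and no exception is written for it. A required schedule does not prevent late visits. The remark about unscheduled visits also bears on the remedy: unscheduled records prompted by toxicity must not replace scheduled ones.

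**Conclusion.** The point holds in a limited form. Read as written, SAP 4.3 excludes off-window records from the by-visit summaries in step 1, with no fallback. The exclusion is informative if toxicity displaces visits unequally between arms. Whether it does, by how much and in which direction cannot be determined from the documents.

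A reader might go further and infer that the SAP discards every off-window measurement, or that by-visit means will flatter cabozantinib. The documents support neither inference. Off-window values remain in the data and in the unfiltered analyses of step 6. The toxicity condition appears in one place, covers safety visits only, and sits beside text that keeps the schedule during interruptions. No displacement rate or score deficit is given. The 59% of patients with a dose reduction in the earlier HCC cohort (protocol 1.3.3.3.1) is not a rate of late visits, and that cohort started at 100 mg.

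The consequence is confined to descriptive safety tables, exploratory by-visit summaries and the EQ-5D-5L t-tests by time point. The questionnaire completion rate could also be affected if a completed but off-window form is not counted. The primary and secondary conclusions do not depend on this.

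**What to change.** In SAP 4.3, name the summaries that are organized by visit and replace the exclusion with one of two rules: contiguous analysis windows running from midpoint to midpoint between scheduled visits, or the nominal scheduled visit under which the record was collected. Build the windows on each assessment's own schedule, anchored to W1D1 for safety and EQ-5D-5L and to randomization for AFP and Child-Pugh. For example, the Week 3, 5 and 7 safety visits have target Dose Days 15, 29 and 43, so the Week 5 window runs between (15 + 29)/2 = 22 and (29 + 43)/2 = 36.

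Within a window, give scheduled records priority over unscheduled ones, then take the record closest to the target day. Report out-of-window counts by arm and visit, so that unequal displacement can be seen. Separately, reconcile protocol Appendix A with section 5.2 on whether the safety-visit windows depend on absence of toxicity.

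The cost is a revised SAP paragraph and a standard windowing program, approved before unblinding as SAP 4.8 requires for substantive changes. The downside is that some records will lie further from the nominal day: up to half the interval, so 7, 14 or 28 days for 2-, 4- and 8-weekly schedules.
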